Study Protocol and Statistical Analysis Plan

EFFECTIVENESS OF COMBINED AEROBIC AND STRENGTH TRAINING IN ACUTE AND CHRONIC ADAPTATIONS IN PATIENTS WITH HEART FAILURE

Date: 19/10/2017

PROTOCOL

Title

Effectiveness of combined aerobic and strength training in acute and chronic adaptations in patients with heart failure

Participants

Patients with chronic heart failure (CHF) that underwent to a hospital-based cardiac rehabilitation (CR) program in the Lisbon district Hospitals will be recruited. The study will be performed in the Cardiovascular Rehabilitation Center of the University of Lisbon (CRECUL) at the Lisbon University Stadium (EUL). The participants will be randomized into one of the following exercise groups: A) combined exercise training with more aerobic training and less strength training (CAT); B) combined exercise training with more strength training and less aerobic training (CST); Inclusion criteria: CHF patients; receiving optimal medical therapy for CHF (including an angiotensin-converting enzyme inhibitor or an angiotensin receptor blocker and a beta-blocker unless a contraindication is evident) with a stable condition for more than 1 month (no hospitalization for heart failure (HF), no change in medication, and no change in New York Heart Association (NYHA) functional class. Exclusion criteria: if they are younger than 18 years or are unable to sign informed consent; unstable angina pectoris; and orthopedic or neurological limitations to exercise. Patients will be stratified (by age and etiology) and randomized consecutively to CAT or CST in the beginning of the exercise at community. There will be 2 assessment moments (M): M0) before starting the exercise training (ExT) program (baseline) and M1) 3 month after starting the ExT.

Sample size was calculated (G-Power, Version3.1.3) assuming a difference in carotid intima-media thickness (IMT) between groups of 5% to be a clinical important difference with a SD of 0.16, $\alpha=0.05$, $1-\beta=0.95$ and an expected dropout rate of 26%. The calculations yielded a total minimum sample size of 28 participants (14 in each group).

Recruitment

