ExT is a major component of rehabilitation/secondary prevention interventions, inducing significant beneficial changes in mechanisms of pathophysiology, exercise tolerance, functional capacity and QoL, while a positive impact on hospitalization and mortality reduction. There has been growing interest in the characteristics and modalities of exercise training able to induce optimal benefits. High intensity and interval mode have been shown to induce greater benefits than moderate intensity and continuous mode regimes. Considering the current body of evidence of high-intensity interval training (HIIT) in CHF, HIIT demonstrated to be more efficient, result in long term adherence, which be an important practical aspect to consider during the ExT and consequently optimized improvements in central and peripheral adaptations [25]. More studies are needed to proof their safety and benefits on this type of patients.

Additionally, there has been sound rationale for the inclusion of ST to the HIIT, which has been also shown able to yield benefits in terms of exercise capacity and QoL. It is well known that combined AT and ST is the preferred exercise intervention to reverse or attenuate the loss of MM and improve exercise and functional capacity, muscle strength in this individuals [19]. But there are underlying mechanisms from the ST in the CHF patient's peripheral capacity that remains unidentified. And isn't known what is the benefits of combine different proportions of AT and ST.

For that reason, the investigators will test two proportions in combined training, CAT and CST. There haven't been any data on the so called combined regimes, which include both aerobic exercise with HIIT and ST and the investigators will evaluate the effects of acute and chronic response.

PURPOSE

The research project will contribute to a better understanding in several aspects that are unexplained by scientific research. The purpose of this research project are:

- 1) To determine the effectiveness of a ExT programme with different proportions of CAT and CST in promoting cumulative effects in acute and chronic adaptations in CHF patients;
- 2) To identify the mechanisms of the potential improvement in effectiveness promoted by ST;

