This research project is going to employ state of the art methods focusing peripheral adaptations analysis in both groups namely in echocardiography variables, cardiopulmonary exercise testing, arterial stiffness, functional physical fitness, QoL and body composition in 2 distinguished moments: M1) baseline and M2) 3 month.

Plan and Methods

This project will assess the acute and chronic effects in central and peripheral adaptations of a combined training to patients with CHF would address a number of important breaches in scientific knowledge with potential clinical benefits.

STUDY DESIGN

A longitudinal randomized control trial (RCT) research design using two distinct ExT prescriptions (CAT and CST) will be applied in CHF patients. All the same assessments will be done in two moments: M0 - baseline and M1 - 3 months after starting the ExT. The patients will be randomized into either one of the two ExT group.

Recruitment and screening will last 9 months (September 2017 to May 2018) and the patient assessment will last until August 2018. It is expected to finish the project with peer-review redaction submitted and/or accepted in December 2018 (time line attached).

The following assessments on the 4 moments will be performed at the Pulido Valente Hospital, FMH-UL and Academia de Fitness at EUL: Echocardiogram (Echo) (MyLab Alpha, ESAOTE);

cardiopulmonary exercise test (CPET) (Ergostik, Geratherm Respiratory GmbH, Bad Kissingen); arterial stiffness - Complior Analyse (ALAM Medical); Intima-media thickness - ultrasound (ESAOTE MyLanOne); body composition - dual energy radiographic absorptiometry (DXA, Hologic Explorer-W); functional physical fitness - Fullerton Functional Fitness Test; isometric strength – portable hand dynamometer JAMAR plus digital (Sammons Preston); maximal strength – 1RM and QoL questionnaire.

All assessment moments will be done in 5 days:

Day 1 – Echo will be performed at the Pulido Valente Hospital;

Day 2 and 3 – during one day and time of the ExT session at the EUL, the patient will perform the functional physical fitness tests; maximal strength; isometric strength and QoL questionnaire. In other day the investigators will perform the arterial stiffness and the IMT before the session in rest and after the ExT;

Day 4 – In FMH, the CPET and dual energy radiographic absorptiometry (DXA) exam.

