4. INTIMA-MEDIA THICKNESS

Carotid intima media thickness (cIMT) will be defined as the distance between the leading edge of the lumen–intima interface to the leading edge of the media–adventitia interface of the far wall of the right carotid artery using an ultrasound scanner equipped (ESAOTE MyLanOne) with a linear 13 MHz probe and implemented with a previously validated radiofrequency-based tracking of arterial wall that allows a real-time determination of common carotid far-wall thickness with high spatial and temporal resolution [26]. cIMT is automatically measured, and distension curves are acquired within a segment of the carotid artery about 1 cm before the flow divider, where the operator places the region of interest. The coefficients of variation for repeated measurements in our laboratory for cIMT and diameter are reported elsewhere [26].

To evaluate the acute effects of ExT, at the pre-exercise measurement at 15 and 30-minutes rest, blood pressure (BP) was measured twice on the right upper arm using an automatic cuff in a dorsal decubitus position. If the difference in systolic BP (SBP) between the two measurements was larger than 10 mmHg, another BP measurement was performed. The final measured value was used for the analysis. Immediately after measuring BP. Post-exercise measurement was carried out with the same methods.

From this test, the investigators will study the diameter and distensibility of the artery, intima–media thickness in the carotid arteries (cIMT), PWV, brachial blood pressure, and the alpha and beta index.

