9. MAXIMAL STRENGTH

Maximal strength will be assessed by 1RM test for each of six weight exercises on variable resistance machines (Life Fitness) available at the EUL as follows, leg press, leg extension, leg curl, low row, chest press and lat pull down. The protocol test of 1RM was determined as previously described in our prior studies[27]. The protocol will include four pre-test sessions to familiarize each patient with the test procedures. Correct exercise and breathing techniques (avoidance of the Valsalva manoeuvre) will be practiced. Prior to the 1RM determination, each subject warmed-up for 15 min on a treadmill at 50% of HRR and then performed ten stretching exercises. To warm-up before using a machine, each patient will be asked to perform eight repetitions using a relatively light resistance, followed by a 30 second rest. A second set of four repetitions using a moderate resistance will be then used, followed by a 1 minute rest. After that each patient will be asked to perform single repetitions until the 1RM was reached. The rests between attempts will be 1–2 min. The resistance will be increased by approximately 5 kg, or by 2.5 kg when the subject was near his maximum. Strength will be recorded as the maximal number of kilograms lifted in one full range of motion. The order of the tests will be the same for all patients, and these exercises will be the same as those used for the ExT.

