11. EXERCISE TRAINING PROGRAM

The ExT program will be carried out mostly in groups at the EUL gymnasium, 3 or 2 times a week (depending on the availability of the patient for complete the 90% of prescribed sessions), 60 minutes per session, on non-consecutive days and supervised for both groups. All sessions will include 10 minutes of warm up and cool down standardized for both groups. The warm up will focus on pulse raising, mobility and preparatory stretching for the conditioning component. Cool down will include transition from conditioning component to the stretching phase, which comprises static and dynamic stretching exercises for all major muscle groups. Muscle strength is intentionally performed before the aerobic exercises to maximize training effects. Sessions will be deemed completed when at least 90% of the prescribed exercises have been successfully performed.

All patients will do in the strength part the same 6 machines (3 to the upper limbs and 3 for de lower limbs): leg press, leg extension, leg curl, low row, chest press and lat pull down. The periodization created allows for a slow progressive increase in strength exercise intensity, volume and density(effort/rest).

CAT group: The subjects will perform in ST part, always only 1 set in the 6 machines early mentioned. During the first and second week they will do 12 repetitions at 40% - 50% of 1 RM. In the third and fourth week progress to 10 repetitions at 60%-70% of 1 RM, and in the second and third month, 8 repetitions at 70%-80% of 1 RM. In the AT part the HIIT protocol is based on a ratio 2 min : 1 min. Consisted of 10 interval training periods (2 min of high intensity at 85% - 90% of heart rate

reserve (HRreser) and 9 pauses (1 min in passive pause) between interval training periods. During the first week of training will start with a continuous training, in the second week the investigators will start with 5 intervals of HIIT, and in the second and third months they are doing the 10 stages of HIIT.

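### The exercise session behind the before/after vascular readings is not fixed at M0 and M1; if the prescribed sessions are used, a changed acute response cannot be read as training adaptation

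*Combined protocol and SAP*

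**What the plan says.** The Participants section sets two assessment moments: "M0) before starting the exercise training (ExT) program (baseline) and M1) 3 month after starting the ExT". Purpose 1 is to judge the two training mixes "in promoting cumulative effects in acute and chronic adaptations in CHF patients", and acute adaptation is also in the title.

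Under STUDY DESIGN, the description of Days 2 and 3 reads: "In other day the investigators will perform the arterial stiffness and the IMT before the session in rest and after the ExT". The same section adds: "All the same assessments will be done in two moments: M0 - baseline and M1 - 3 months after starting the ExT". Section 4 (Intima-media thickness) gives the reason for the paired readings and their method: "To evaluate the acute effects of ExT, at the pre-exercise measurement at 15 and 30-minutes rest, blood pressure (BP) was measured twice", and later "Post-exercise measurement was carried out with the same methods". No time after exercise is stated separately.

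Session content appears only in section 11, as the training prescription for each arm. Section 9 mentions some attendance before strength testing: "The protocol will include four pre-test sessions to familiarize each patient with the test procedures". It does not link those sessions to the vascular readings.

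Section 13 compares means within and between groups for all outcomes. It uses a mixed ANOVA with a two-level pre/post factor and a mixed-model comparison of M0 with M1. It does not say whether resting or post-session values enter either model.

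**The concern.** An acute response is a response to a particular bout of exercise. To compare acute responses three months apart and attribute the difference to training, the bout must be the same on both occasions. The plan repeats the measurements but does not fix the bout, and the documented sessions change during the programme by different amounts in the two arms.

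What is at stake is the acute half of purpose 1. If the post-minus-pre change in pulse wave velocity, carotid IMT or blood pressure differs between M0 and M1, the cause could be adapted vessels, a different session that day, or both. Nothing in section 13 separates these or stops the result being reported as adaptation.

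**Working it through.** The plan gives no figure of its own on this point. The check has three steps.

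**1. Is the bout identified anywhere?**
- STUDY DESIGN: readings are taken around a session whose content is not given.
- Participants: M0 comes before the programme, so as defined no prescribed session has yet taken place.
- Section 4: rest times before exercise and a matching method afterwards, but no session content.
- Section 9: familiarisation sessions make earlier attendance possible, but none is named as the M0 bout.
- Section 11: the only documented content, and it starts with week 1 of training.

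The bout is therefore not identified at either moment.

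**2. How much do the documented sessions change and diverge?** Inputs are from section 11. Strength volume-load per session = 6 machines × sets × repetitions × fraction of 1RM. Interval work = number of intervals × 2 min.

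| Period | Arm | Repetitions | Volume-load, mid-band (range) | Interval work |
|---|---|---|---|---|
| Weeks 1-2 | both | 6×1×12 = 72 | 72×0.45 = 32.4 (28.8-36.0) | week 1: continuous, dose not stated; week 2: CAT 5×2 = 10 min, CST 3×2 = 6 min |
| Months 2-3 | CAT | 6×1×8 = 48 | 48×0.75 = 36.0 (33.6-38.4) | 10×2 = 20 min |
| Months 2-3 | CST | 6×3×8 = 144 | 144×0.75 = 108.0 (100.8-115.2) | 5×2 = 10 min |

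The CST/CAT volume-load ratio in months 2-3 is 108.0/36.0 = 3.0. Across the load bands it runs from 100.8/38.4 = 2.63 to 115.2/33.6 = 3.43. Interval work is 10 v 20 min, a ratio of 0.5.

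These figures describe what is done in a session. They do not measure vascular effect. The weeks 1-2 row shows that content changes during the programme; it is not evidence of what is done at M0.

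**3. What does the change in acute response then estimate?** Take an additive approximation with the prescribed sessions in use. For arm g, let A_g be the adaptation in acute response, and let S_g0 and S_g1 be the effects of the sessions used at M0 and M1.

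- Within an arm, the M0-to-M1 change in (post − pre) = A_g + (S_g1 − S_g0).
- Between arms, the difference in that change = (A_CST − A_CAT) + (S_CST,1 − S_CAT,1) − (S_CST,0 − S_CAT,0).

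Even if the M0 sessions were alike, so that the last bracket is zero, one observed contrast still carries two unknowns. If each arm repeats the same session at both moments, S_g1 − S_g0 = 0 and the within-arm change reduces to A_g. Resting values taken before the session contain none of that day's S terms.

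**The case against.** The strongest reply is that the plan never states the contrast in question. Section 13 compares M0 with M1 and arm with arm; it does not define a difference of differences. Its ANOVA sentence gives the purpose as judging the programme, which favours reading the pre/post factor as M0 v M1. This stands: the factor is not freely open to every reading, though which values fill it remains unsaid. It does not remove the problem. Acute adaptation is a stated aim, section 13 covers all outcomes, and a change in acute response is the natural quantity to report under that aim.

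A second reply is that repeating all the same assessments implies the same session. It may have been meant so, but the sentence covers assessments, and the bout is never described.

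A third is that the arms' sessions are meant to differ, because that is the randomised treatment. This also stands. A reader might infer that the M1 comparison of acute response between arms is confounded. It is not: it validly compares regimens, meaning the allocated session after three months of that training.

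A reader might also infer that a threefold volume-load ratio implies a bias of similar size, or that the M0 and M1 sessions are known to differ. The documents support neither. Volume-load is not a vascular measure, M0 content is unknown, and no bias in any outcome can be calculated from the text.

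**Conclusion.** The concern holds, conditionally. The gap in the text is certain: no session is named for M0 or M1. The consequence depends on the prescribed sessions being used. In that case the M0-to-M1 change in post-minus-pre response, and its arm difference, mixes adaptation with session content that in months 2-3 differs about threefold in strength volume-load (2.6 to 3.4) and twofold in interval work. The direction and size of any bias are unknown.

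A reader might go further and conclude that the vascular results as a whole are compromised. The documents do not support that, because resting comparisons of M0 with M1 do not depend on the session. The point deserves correction because it decides whether the acute part of purpose 1 can be answered.

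**What to change.** 1. **Chronic effect (section 13).** Use one prespecified pre-session resting value per outcome, and compare CAT with CST at M1 adjusted for M0.
2. **Acute effect (section 13).** Compare the M1 post-minus-pre change between arms as randomised, at a fixed time after exercise. Where each arm does its own session, describe the result as a comparison of regimens.
3. **Session identity.** Reconcile the Participants and STUDY DESIGN sections with sections 4 and 11 by stating which session is used at each moment and whether it is the same. Unless it is the same, report the M0-to-M1 change in acute response descriptively and do not interpret it as adaptation.

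The cost is one protocol statement and revised analysis wording, with no new measurements. The downside is that the claim of a training-induced change in acute response is given up if the sessions differ. The same applies if M0 readings have already been taken around unstandardised sessions. That is possible, since recruitment was planned from September 2017 and the document is dated 19 October 2017.

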1. ECHOCARDIOGRAM

A resting transthoracic echocardiogram will be performed with MyLab Alpha, ESAOTE, Italy. The exam will be performed by the echocardiography laboratory cardiologists, who will be blinded to experimental protocol and group randomization, with the usual measurements of systolic and diastolic function, particularly the calculation of LVEF by Simpson's formula, telediastolic and telessystolic volumes and diameters, doppler analysis of the transmitral flow, tissue doppler and quantification of mitral valve regurgitation.

2. CARDIOPULMONARY EXERCISE TEST

CPET is the best technique to obtain the maximal functional capacity. This test will be performed with the subjects in a non-fasting condition and under the regular medication.

Symptom-limited exercise test

A symptom-limited ramp incremental CPET, will be performed on a cycle ergometer (Ergostik, Geratherm Respiratory GmbH, Bad Kissingen, Germany) with breath-by-breath gas exchange measurements. For cardiorespiratory recording will be used a mask that does not interfere with breathing and can cause discomfort. Gas exchange analysis provides a highly reproducible measurement of exercise limitation and insights into the differentiation between cardiac or respiratory cause of dyspnea, assesses ventilator efficiency and carries prognostic information. After 2 minutes rest followed by 3 minutes unloaded pedaling, each patient will be encouraged to exercise to exhaustion, as defined by intolerance, leg fatigue or dyspnea unless clinical criteria for test termination occurred. Patients will continue seated on the cycle ergometer as soon as they stop, while recovery measurements are taken. Blood pressure will be recorded at baseline, during each stage, at peak exercise and during recovery. Peak oxygen capacity will be considered the highest attained VO_2 during the final 30 sec. of exercise and ventilator AT will be estimate by the V-slope method. Heart Rate (HR) recovery as a simple marker of parasympathetic activity will be calculated as the difference between peak HR and HR one minute later. The recovery period will continue until 6 minutes after peak effort. Chronotropic response (ChR) to exercise will be evaluated by the % of HR reserve (HRR) used at peak exercise. $\text{ChR} = [\text{peak HR} - \text{resting HR}/(220 - \text{age} - \text{resting HR}) \times 100]$. A failure to use 80% of the HRR is defined as chronotropic incompetence. All patients should achieve a respiratory exchange ratio of >1.1 , an indicator of maximal effort in the CPET. The CPET will provide clinical information to patient screening and exercise intensity prescription.

The investigators will study, the HR max and recovery at 1st and 3rd minutes, the VO_2 peak, respiratory exrespiratory exchange ratios, respiratory quotient, ventilatory anaerobic threshold, the ventilatory equivalent for O_2 and CO_2 .

3. ARTERIAL STIFFNESS

Arterial stiffness will be measured by pulse wave velocity (PWV) obtained by applanation tonometry will be measured during a 15 and 30-minute rest. A single operator locates the carotid, femoral, radial and distal posterial tibial arteries on the right side of the body and mark the point for capturing the corresponding pressure curves with two specific pressure sensitive transducers. The distance between the carotid and femoral, radial and distal posterial tibial arteries will be measured directly and entered into the Complior Analyse software (ALAM Medical, Paris, France). Right brachial blood pressure will be measured and entered into the Complior Analyse software, and then

signal acquisition is launched. The operator position the carotid sensor with the help of its specific holder and manually held the femoral sensor on the femoral artery and the distal sensor in the distal posterial tibial artery. When the operator observes 10 carotid pulse waveforms of at least 90% quality showed on the software, simultaneous carotid and femoral, radial and distal posterial tibial pressure curves will be recorded for 10 pulse waveforms. The time delay (aortic transit time) between the two pulse waveforms is then calculated automatically. Values obtained from the carotid to femoral artery, carotid to radial artery and carotid to distal posterial tibial artery are taken as indices of central/aortic, upper and lower limb arterial stiffness, respectively. The investigators will study the pulse pressure (PP), the carotid stiffness index β , augmentation index (Aix), and peak wave velocity (PWV)

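### The lower-limb stiffness index (carotid-to-tibial pulse wave velocity) includes the segment labelled central/aortic, so this one index mixes aortic and leg stiffness

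*Combined protocol and SAP*

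**What the plan says.** Section 3 (Arterial Stiffness) defines three indices by path. Carotid-femoral PWV stands for central/aortic stiffness, carotid-radial for the upper limb and carotid-tibial for the lower limb: "carotid to distal posterial tibial artery are taken as indices of central/aortic, upper and lower limb arterial stiffness". No femoral-to-tibial index is defined there or elsewhere, and no subtraction of the carotid-femoral segment is planned.

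The same section describes the raw measurements:

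- Sites: "A single operator locates the carotid, femoral, radial and distal posterial tibial arteries on the right side of the body".
- Distances: "The distance between the carotid and femoral, radial and distal posterial tibial arteries will be measured directly".
- Curves: "simultaneous carotid and femoral, radial and distal posterial tibial pressure curves will be recorded for 10 pulse waveforms".
- Delay: "The time delay (aortic transit time) between the two pulse waveforms is then calculated automatically".
- Equipment: the pressure curves are captured "with two specific pressure sensitive transducers", yet the section then describes a carotid, a femoral and a distal sensor in use.

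The Purpose section describes the project as "focusing peripheral adaptations analysis in both groups" and lists arterial stiffness among several domains. Plan and Methods sets out to assess both central and peripheral adaptations.

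**The concern.** A pulse that reaches the posterior tibial artery has passed the femoral site. The carotid-tibial delay is therefore the carotid-femoral delay plus the femoral-tibial delay. By the section's own labels, the index called lower limb contains the one called central/aortic.

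This has three consequences. A change confined to the aorta also moves the lower-limb index. A change confined to the leg arteries is diluted in it. Agreement between the two indices is partly built in, as is any correlation between them of the kind the Statistical Analysis section plans.

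The distinction is relevant here because the arms load the legs differently. In the second and third months the aerobic-weighted arm does 1 set on each machine and the strength-weighted arm 3 sets. Three of the six machines train the legs. The interval work is 10 against 5 periods. Whether a stiffness response lies in the aorta or in the leg is a natural question for this comparison.

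**Working it through.** The plan gives no PWV figure to reproduce, so the check is path arithmetic on assumed values.

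**Inputs (all assumed; none is in the documents)**

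| Quantity | Range | Central case |
|---|---|---|
| Carotid-femoral distance, Dcf | 0.50-0.65 m | 0.60 m |
| Carotid-tibial distance, Dct | 1.35-1.55 m | 1.45 m |
| Aortic PWV, Va | 8-12 m/s | 10 m/s |
| Leg PWV, Vl | 10-12 m/s | 11 m/s |

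**Formulas**

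- Aortic transit time Ta = Dcf / Va; leg transit time Tl = (Dct - Dcf) / Vl.
- Carotid-tibial PWV = Dct / (Ta + Tl).
- Aortic share of transit time s = Ta / (Ta + Tl).
- A 10% fall in one segment's PWV multiplies its transit time by 1/0.9.

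**Central case**

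- Ta = 0.60/10 = 60.0 ms; Tl = 0.85/11 = 77.3 ms; total 137.3 ms; s = 60.0/137.3 = 43.7%.
- Carotid-tibial PWV = 1.45/0.1373 = 10.56 m/s.
- Aorta alone down 10%: total = 66.7 + 77.3 = 143.9 ms; the index changes by 137.3/143.9 - 1 = -4.6%.
- Leg alone down 10%: total = 60.0 + 85.9 = 145.9 ms; the index changes by 137.3/145.9 - 1 = -5.9%.

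**Extremes, with all ranges crossed freely**

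- Smallest aortic share (Dcf 0.50, Dct 1.55, Va 12, Vl 10): Ta = 41.7 ms, Tl = 105.0 ms, s = 28%. The aorta-only fall shows as 3.1% and the leg-only fall as 7.4%.
- Largest aortic share (Dcf 0.65, Dct 1.35, Va 8, Vl 12): Ta = 81.3 ms, Tl = 58.3 ms, s = 58%. The aorta-only fall shows as 6.1% and the leg-only fall as 4.4%.

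**Leg-only value**

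Femoral-tibial PWV = (Dct - Dcf) / (carotid-tibial delay - carotid-femoral delay). In the central case this is 0.85 / (0.1373 - 0.0600) = 11 m/s. After the aorta-only fall it is 0.85 / (0.1439 - 0.0667) = 11 m/s again, so the aortic change no longer enters.

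**Cost in noise (central case)**

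Assume equal, independent error e in the timing of the wave foot at each site.

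- Carotid-tibial delay: two timings, SD = √2·e, relative error √2·e/137.3.
- Leg delay with all curves recorded together: the carotid timing cancels, SD = √2·e, relative error √2·e/77.3. Ratio to carotid-tibial: 137.3/77.3 = 1.78.
- Leg delay from two pairs recorded in sequence: four timings, SD = 2e. Ratio: √2 × 1.78 = 2.51.
- A true 10% leg fall gives a signal of 10% in the leg-only value and 5.9% in carotid-tibial PWV, a gain of 10/5.89 = 1.70. Signal over timing noise is then 1.70/1.78 = 0.96 times that of carotid-tibial PWV if simultaneous, and 1.70/2.51 = 0.68 times if sequential. Between-patient variation in aortic stiffness, which also enters carotid-tibial PWV, is not counted.

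**The case against.** The strongest reply is that the plan names the path behind each index and reports carotid-femoral PWV beside the carotid-tibial value. In the central case an aorta-only change would show as -10% in one and -4.6% in the other, and an attentive reader could see where it lay. The Purpose section lists many domains and states no hypothesis about leg arteries, and the sample size rests on carotid intima-media thickness. All of this stands, and it keeps the point minor. It does not make a mixed path a lower-limb measure.

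The feasibility objection also stands in part. The section speaks of simultaneous curves, but also of two transducers and of a delay between two waveforms. If only two sites are recorded at a time, the subtraction still works with the carotid as common reference, but not on the same beats and with more noise. The section also does not say by what route the distances are taken. Their difference equals the femoral-tibial path only if the carotid-tibial distance runs through the femoral point.

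Three stronger readings are tempting, and the documents do not support them:

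- A reader might infer that the plan fails to separate central from peripheral stiffness altogether. It does not: the carotid-femoral index contains no leg segment, and nothing here tells against the carotid-radial index.
- A reader might infer that a leg-only value from the same beats is already assured. The conflicting sensor description leaves that open.
- A reader might infer that the leg-only value would detect leg changes better. On timing noise alone it would not.

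**Conclusion.** The point holds for one of the three indices. Carotid-tibial PWV, labelled lower limb, is a whole-path measure that includes the segment the plan calls central/aortic. The direction follows from the plan's own definitions. The size rests wholly on the assumed distances and velocities: an aortic share of 28-58% of the transit time, an aorta-only 10% fall showing as 3.1-6.1%, and a leg-only 10% fall showing as 4.4-7.4%.

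Separating the leg segment improves specificity for the central-versus-peripheral question, with about 1.8 times the relative timing noise if the curves are simultaneous and 2.5 times if sequential. Severity is minor, and the sample size is unaffected.

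**What to change.** In section 3 (Arterial Stiffness), before analysis:

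1. Relabel carotid-tibial PWV as a whole-path (aorta plus leg) index and keep it.
2. Report beside it a femoral-tibial PWV = (carotid-tibial distance - carotid-femoral distance) / (carotid-tibial delay - carotid-femoral delay), with the carotid as common reference.
3. State how many sensors are used and whether the femoral and tibial curves are recorded together or in sequence, and reconcile the two-transducer wording with the three sensors described.
4. State the route by which each distance is measured, so that the subtraction of distances is valid.

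The cost is one derived variable and a few sentences, with no new test. If only velocities and distances are kept, each delay is distance divided by PWV, provided no scaling has been applied. The downside is the extra noise shown above, which is why the derived value should be added to the carotid-tibial index and not replace it.
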